#### Inclusion criteria:

- Ages Eligible for Study: Over the age of 18
- Sexes Eligible for Study: All
- First-time ischemic or haemorrhagic stroke, as documented by a CT or MRI
- Patients able to sit for at least ten minutes and to look after own affairs without assistance i.e. a Modified Rankin Scale (MRS)≤ 2
- Montreal Cognitive Assessment (MoCA) ≥12
- Ability and willingness to participate in the study
- Complete a signed consent form

Exclusion criteria:

- Significant medical conditions that affected function prior to the stroke and would limit normal stroke rehabilitation (e.g. musculoskeletal condition affecting arm function or cardiac condition limiting basic activities of daily living).
- Bilateral weakness of upper extremities
- Unavailability of a caregiver
- Participation in another clinical trial involving rehabilitation (recreational therapy, occupational therapy, physiotherapy) or an investigational drug.

## Methodology

At the trial site, the sponsor of the study will contribute to pay “dedicated figures”, a member of the clinical care team with a specialisation in clinical research (either a nurse or a physiotherapist) selected by the trial site personnel itself, as indicated by the scope of the Magic project [5]. Such figures will be the only people who will have access to all patient clinical records during the whole research study period, including the screening for patients. The dedicated figures will be educated by the sponsor (CoRehab) before starting the study in order to become a WeReha’s expert. They will be instructed on managing technical issues and details regarding the general functioning of the device (how to navigate the device, how to recharge the tablet and the sensor, how to position the sensor inside the objects and how to use them during game, how to wear the sensor) and for additional support they will be provided with a detailed manual for reference. . The sponsor will provide remote support to patients once at home in the first instance using a specific UK telephone number that will be provided to all participants. The WeReha software and manual will also have this phone number. The sponsor will inform the PI of all communication with participants and identify if this was technical (e.g. how to recharge the sensor, what to do if the system seems to be frozen and does not respond, what to do if the sensor does not switch on) or clinical. If it is a clinical difficulty then the PI will make contact with the participant. The dedicated figures will be provide training to patients and caregivers before receiving the device and go home.

Recruitment will start when patients are still in hospital after the onset of their stroke, as early rehabilitation can provide to better results. Whenever a patient is informed about the study or requests information and the inclusion/exclusion criteria are met, the dedicated figure will report that a patient could be enrolled in the study. If a patient accepts to partecipate in the study, he/she have to sign the appropriate documentation within 48 hours.

Only after the dedicated figures have enrolled the patient and the signed consent form is completed will a participant be registered on the WeReha system through the dedicated clinical web application. Patient and the caregiver(s) will then receive appropriate training from the dedicated figures with a device similar to the one they will be using at home. The training will take place in the facility where the patient has been enrolled and it will be carried out by the dedicated figure. This will take the form of an education session aimed to provide the patient and the caregiver with all the technical information required for the correct usage of the device. All participants will also be taught how the biofeedback exercises works in terms of games graphics, goals, bonus, scores as well as how to understand if the movement performed is correct or not. The caregiver is instructed in helping and supporting the patient when required and how to make contact with the supervisor in case assistance for the device is required. Both the patient and the caregiver, before leaving the facility, will be provided with a user manual for WeReha's usage at home. Based on our experience during the feasibility work, this training will last a minimum of 30 minutes up to a maximum of 60 minutes). The dedicated figure will then input the information about the patient into the WeReha web application, together with the results obtained in scores, and scales, resulting in the creation of a rehabilitation protocol, validated with rehabilitation professionals, which will then will be assigned to the patient. In cases where the participant remains in hospital for longer than expected, they will be permitted to use the device in this setting. Use of the device in this setting will not be included in the 20 weeks of usage.

Following discharge, participants will be reviewed in their own environment by the PI to ensure that the device is set up appropriately so that they can perform the exercises assigned. Participant usage of the device will be monitored at eight weeks. If at this stage the participant has not had four active weeks then the PI will review the patient with the expectation of the device being returned. In certain cases patients may have been unwell for a prolonged period and unable to use the device and it will be left to the PI to decide whether to remove the device or to allow the patient to continue using it for the full 20 weeks. All participants recruited to the study will be asked to complete the Technology Assessment Model questionnaire. After 20 weeks, the patient will return the WeReha device and the designated person will complete final assessments (clinical evaluation and questionnaires).

Identifiable data will be retained for the whole research study period. The data retention policy is clearly stated in the Patient Information Sheet. Since the Community Stroke Team provides therapy to patients, the team will highlight any capacity/ safety issues at any time and will then manage the patient to ensure safety.

Once the WeReha is returned to the hospital after being used by a patient, the dedicated person will follow a specific procedure in order to make the device available for any future usage by another patient. This procedure consists of resetting data through the specific button in the administration area of the software and cleaning as per infection control procedures for all the

reusable HW components. Also, new single use components (straps and smart objects) will be prepared for a new patient, so that the device is completely reusable.

Throughout the study, WeReha will suggest exercises in different forms to support rehabilitation of the most important body functions.

1. Video guided and biofeedback assisted exercises are proposed for balance intervention, legs and arms reinforcement and range of motion improvement especially for the foot, ankle, arms and hands. Depending on the exercise, patients are asked to wear one inertial WeReha sensor on the trunk, on a leg, on the foot or on the wrist in order to detect the movements in real time and provide subjects with visual and auditory feedback immediately. The daily sessions is structured in such a way that patients need to change settings and the position of the sensor as little as possible and exercises are grouped in sequences that support this approach. Standing exercises will be proposed only if a caregiver can assist the patient in order to prevent potential falls and minimize patient risk. Clear indications in written form as well as through audio and video tutorials are provided to set up an environment that ensures safety and fall prevention (e.g. the patient is asked to position himself/herself in the corner of a room with a static chair in front of him/her).
2. A WeReha kit also contains three simple objects, an hourglass, a plate and a joystick, through which the patient can practice some functional movements for the hand and the arm. Each object has a spot where the WeReha inertial sensor can be positioned and the object itself becomes "smart". Through these smart objects, patients will be asked to play some simple, interactive and motivating videogames that require them to perform daily functional tasks (such as pouring the water, spinning an object on the table, move the hand with precision...) through which they will exercise arms and body posture improving their personal abilities. These videogames will also prompt the patient proposing simple tasks to solve the games challenge.

It is also important to highlight that patients will gain points and increase their score any time they perform a game/exercise with bonus points being given the more correctly the exercise is performed. By accumulating points patients will receive bonuses and rewards, in order to improve motivation and gain retention.

Every exercise and game has three different levels that correspond to a higher difficulty in performing that task. In the first level, patient will gain 50 points for every correct movement, at the second 100 points and at the third 150 points. Points are accumulated throughout the execution of the exercise and the final score is shown at the end of the exercise itself. In order to move to the level above, patients need to execute the required movement correctly for a specific time or a number of repetitions. The level above will require the performance of a more precise and at the same time more rewarding task. As an example, in stability exercises the patient is required to stay within a specific range shown as a target on the screen while the center of mass, shown on the screen as a moving circle, is measured by the sensor worn at the trunk. For every 0.5 degrees that the patient stays within the required range, they are rewarded 50/100/150 points

(depending on the current level). Initially, at level 1, the target is within a range of +/- 15 degrees both in sagittal and frontal planes and the patient is rewarded 50 points every 0.5 degrees. If the patient stays within the range for a total of 15 degrees then the patient is required to stay within a range of +/- 12 degrees (level 2) in both directions and is rewarded 100 points every 0.5 degrees. If again they stay within the new range for another 15 degrees, the target becomes +/- 10 degrees and the points accumulated are 150 every 0.5 degrees.

Also, whenever an exercise is completed, the patient receives a star as a reward for finalising a task, meaning the exercise is executed for the whole time required without skipping it. The combination of scores and stars is then shown at the beginning and at the end of every session. These results and scores have been well received by patients and clinicians during the feasibility work and have been recognised to be a simple but effective motivational aspect of the use of the device. In case the patient needs more details, the staff can always send a more detailed report via email through the web application.

## Safety Considerations

Definitions regarding adverse events are as follows

- Adverse Event: An AE is any untoward medical occurrence in a study participant.
- Unexpected Adverse Reaction: There are no potential adverse reactions to the study activity known so any untoward or unintended response to the study activity will be classified as unexpected.
- Serious Adverse Events: Any adverse event that results in the following:
  - death
  - life threatening events
  - prolongation of existing hospitalisation
  - readmission to hospital
  - persistent or significant disability or incapacity

Causality (the determination of the relationship between an AE and the study activity) will be made by the Chief investigator.

All AEs that occur between the signing of the informed consent form and the last visit will be reported in the CRF using a proforma to classify the nature and severity of the event. AEs will be followed up routinely.

For all AEs, the investigator will obtain information to determine the outcome of the AE and to assess whether it meets the criteria for classification as a SAE, requiring immediate notification.

The start date, duration, intensity, any relationship to the study, actions taken and outcome will be documented using the trial AE reporting proforma.

All serious adverse events or unexpected reactions that occur between the signing of the informed consent form and the last visit will be reported immediately upon knowledge of the event occurring to both the Chief Investigator and sponsors. It will also be reported in the CRF and outcomes will be tracked and followed up.

Causality and expectedness will be assessed by both the Chief investigator and the Sponsor. The sponsor shall keep detailed records of all serious adverse events relating to the trial.

Safety of patients in home environments is one of the main pillars on which WeReha has been built. Considering the patient vulnerability and the uncertainty around supervision while exercising at home, previous feasibility work in a hospital setting to simulate home environment conditions has been undertaken from the 1st February 2018 to the 30th March 2018. The goal was to examine if WeReha can be intended to be used at home setting, if user interface and exercises were appropriate for stroke survivors and if the patient safety is guaranteed.

In total twenty volunteers in a subacute phase who suffered a stroke (13 males and 7 females, mean age of 63+/- 12 y, event occurred on average 1.2 years before this investigation) have been enrolled at Centro di Riabilitazione “Franca Martini” in Trento (Italy), a private health care facilities who treats neurological outpatients. Each volunteer received 1 session a week with WeReha for one month (4 sessions in total). Each session lasted 30' minute or more, depending on patient's ability. A dedicated physiotherapist was chosen as a supervisor for educating patients on the usage of the device before the first session and supervising them during each session, also to provide us with important feedback about exercises and games provided. At this aim, he was provided with all the instructions needed on the usage of the device before starting the study. Two days a week were scheduled in order to have all the volunteers performing the session with WeReha (10 of them a day).

Patients were trained on biofeedback exercises for balance, upper and lower limbs mobility and exercises with the three smart objects for the hand and upper limb. The exercises sequences at each session were the same for all patients. Exercises were changed at every session in order to assess as many exercises as possible among those of the WeReha's library.

Only the first session was actively supervised by the physiotherapist, while during the others the supervisor stayed on the sidelines and intervened only if required. CoRehab staff was observing the study in a completely passive way to record all the interventions required to help volunteers before and during the exercises. After each session all the volunteers were asked to answer to questionnaire about the set-up, the software navigation and the exercises proposed. Each question required an answer with a rating on a scale of value from 1 to 5, where 5 means “Very good” and 1 means “very bad”. The main topics were: the effort on wearing the elastic straps (trunk, thigh, foot and wrist), usability of the software user interface, understanding of video

tutorials and instructions of exercises, software navigation and interaction, understanding of games, ease-of-use to handle the “smart objects”, effectiveness of feedback provided during game, patients attitude with respect to exercises to be performed by themselves or with the aid of a support. Only at the end of the last session patients were asked if they appreciated this innovative and technological home rehabilitation solution and how long they would have used the device willingly.

Furthermore in order to receive as much feedback as possible from the clinical point of view, WeReha was also evaluated by a professionals group (2 physiotherapists, 1 psychiatrist and 1 psychologist) of another private clinic, Fondazione Santa Lucia in Rome, where the staff have a great experience in stroke patients rehabilitation with technology. We asked them to test the device on their own (not on patients) and to answer the same questionnaire underwent to Franca Martini’s patients from a clinical point of view.

After the two month study period all the answers from the two sites and the comments from Villa Martini’s patients were collected and evaluated. Particularly, WeReha has been evaluated to be a simple and easy-to-use device for stroke patients, even for those who do not have much experience with technological devices (pc, tablet, smartphone...). The first day of training on the usage of the device seemed to be sufficient to guarantee an independent use by patients, especially with regards to the software navigation. It has also been described as motivational and fun by patients, so much so that they would continue the training with WeReha at home on average three months without finding it boring and repetitive. Most importantly, the indication to use the device for 3 months was also provided by clinical staff supervising the feasibility study in both sites, and this is the reason why we have set the maximum time frame to 12 weeks.

However some difficulties have been encountered by volunteers in the set-up and in understanding the exercises tutorial: wearing the Velcro band at the trunk alone seemed to be a difficult task for the majority of them (17 out of 20), the scientific terms (i.e. hip abduction, hand supination/pronation...) used when referring to exercises were not understandable (14 out of 20) and video tutorials seemed to be too long and with too much information to be understood at once (11 out of 20). Furthermore the clinicians agreed on excluding exercises in standing position without supervision of a caregiver.

Considering this feedback, WeReha has been improved as of the first week in April. We consider feasible and reasonable that WeReha can be used for rehabilitation in home environment, as long as the patient safety is ensured while using the device without the caregiver’s supervision. In order to ensure this condition, we added a specific question at startup of the application about the presence or not of a caregiver, so that exercises in standing position are allowed only under supervision as well as exercises requiring the strap on the trunk even if in sitting position.

Furthermore in order to improve the understanding of the exercises, the instructions and the tutorial language have been revised and all the scientific terms have been replaced by easier, more colloquial and explicative ones.

It must be reminded that from the web application every exercise can be labelled if a caregiver is required and it won't be proposed to the patient in case the caregiver is absent.

All activities and results carried out in the trial did not raise security/safety issues and that they comply with national and international regulations on dual-use of goods or dangerous materials and substances. Given the target patients were those that satisfy inclusion and exclusion criteria, it is noted that:

- The WeReha device is a class 1 medical device, in agreement to norm 93/42/EEC
- All the components integrated in WeReha are certified for home usage.
- The WeReha system doesn't take any autonomous decision on the rehabilitation setting: the system has been conceived to leave the clinician the ultimate decision on any action performed by the system (e.g. exercise prescription, advice provided to the patient, notification for the clinician/medical expert,...) that may affect directly or indirectly the safety of the patient and the outcomes of the rehabilitation path.
- The system prevents the patient performing exercises if the patient declares during the initial questionnaire that the general healthcare conditions of the day are not satisfactory.
- The system setup is designed in such a way that safety of the patient while performing exercises is ensured, both for the upper and lower body (e.g., preventing falls) as well as ensuring repeatability of exercise conditions in different home environments.
- Usage of webcam or any other video means is not included in WeReha in order to maintain the maximum privacy possible along the home rehabilitation. More specifically, the WeReha application running on the device is configured so the camera of the device is kept locked during the whole time of application execution. The tablet is configured in kiosk mode and only WeReha software and related apps can run on it and patients cannot use it for their own purposes. Also, all tablets will be provided with a safety sticker on the camera to make sure that patients do not feel a threat for their privacy
- Self-assessment questions or the initial questionnaire are only used to ensure an adequate attention level and awareness of progress achieved by the patient and to ensure that the patient can execute the exercise sessions safely and comfortably to the greatest extent. In addition, trained staff with access to the web application have the final decision on everything that is presented to the patient.

## Duration of the study and patient's timeline

The total duration of the study is expected to be approximately 1 year and 4 months, starting at the beginning of September 2018 and ending at the end of December 2019.

Each patient will be required to keep the device for 20 weeks following discharge after which they will return the WeReha device to the hospital. In cases where a participant uses the device for

four of the first eight weeks the device has been assigned, the patient's generated output will be considered as valid.

When a patient starts the evaluation period, some clinical measures will be taken, as well as when (s) he returns the device. Such clinical evaluations are specified in the 'Methodology' section.

## Follow-Up

The product will be provided for a maximum of 20 weeks following discharge to the patient, after which the device will be returned to the PI or the trial site for further usage. Patients are not required to have additional follow up after the study term is completed.

## Data Management and Statistical Analysis

As the primary outcomes of the study are designed to evaluate the impact and acceptance of a new rehabilitative technology for stroke patients, a statistical analysis on the primary outcomes will not be conducted. On the other hand, the study clearly aims to evaluate the number of patients, meeting the inclusion/exclusion criteria that are willing to use this technology and the time they will be using the devices at home. It has also to be noted that this study is part of a research project (Magic-PCP, [5]) where 3 companies will provide their solutions to 1 hospital in Italy and sites in NI, i.e. each company will run a similar trial with identical numbers on different sites. The request and the funding to provide 75 devices on each country and aim at performing a validation on maximum 2 patients per device is a clear requirement of the project. We have then defined the primary and secondary outcomes that we consider crucial for evaluating our proposed technology.

The primary outcome will be evaluated in an anonymised form and considered good if planned KPIs are met or exceeded. Secondary outcomes will be evaluated using an unpaired test to compare pre and post intervention measured values, whereas the Chi-square test will be used to detect the significance of outlier proportions, p values smaller than 0.05 will be considered statistically significant. All calculations will be performed using the Matlab software tool (The Mathworks Inc., Natick, MA, USA). We are also interested in evaluating possible correlations among results for the different groups of patients under examination (male and female <55 years old, 55-70, more than 70) to be better prepared for a future clinical investigation of our device.

All details related to the Data Management are provided in Annex A - Technical Data Management of the present document.

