#### **Primary Outcome Measures:**

- Total number of patients enrolled -> KPI: minimum 50 patients enrolled;
- Total number of active patients -> KPI: minimum 40 active patients;
- Total number of patients who drop off, meaning that started the study and had less than 4 active weeks
- Average number of active weeks for each patient: the average number of active weeks is evaluated as the total number of active weeks divided by the number of patients enrolled -> KPI: 8 weeks (excluding drop off before 4 weeks)
- Activity participation, measured in average minutes per day dedicated to exercises with WeReha (measured during active weeks only) -> KPI: min. 45'/week
- Acceptance of the rehabilitation platform WeReha by the patient, evaluated through a questionnaire completed at the end of the study by every participant who consents to the study (see attachment ... )
- Previous results will be analysed on different age/gender groups. Age groups are: <55, 55-70, 70-85 both for male and female, for a total of six groups. Target would be to enroll patients within these groups as homogeneously as possible, but since we cannot foresee patients distribution there are no KPIs set for this outcome

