connected either through Wi-Fi or cellular network, data will be uploaded to the server through a secure VPN or https protected connection, or at the very latest when the device is returned to the hospital. However, for the sake of the study, we will provide a prepaid internet card to all participants requiring it. Patients data will be always uploaded and maintained in an anonymised form and stored following stringent security and privacy principles.

Data relative to the primary outcome will be collected automatically on the device and uploaded to the server whenever possible. Clinical measurements (such as scales and scores) will be assessed only when starting the study and when returning the device.

WeReha includes a password protected administration area accessible only by the dedicated figure, through which it is possible to manage the reset of data in the local memory once the device is collected and then re-assigned to another patient. In addition, every tablet is provided with a software program installed for a quick and effective remote assistance by the technical staff of the sponsor directly on the patient's WeReha device (Bomgar SW, [www.bomgar.com](http://www.bomgar.com)). This is intended as a second level support to patients and will only be required if the dedicated figure cannot solve the issue on which the assistance was sought. WeReha requires an internet connection at patient home in order to allow Corehab's remote intervention.

Following admission to Belfast or South Eastern Trust stroke units, patients will be pre-screened against the inclusion and exclusion criteria. Those who appear to fulfill the criteria will be highlighted by nurses and therapists to the recruiting therapist. Patients will be provided with all the study details and patient information sheet (PIS) to review. A screening log will be used to track the number of patients that are approached to participate. If the patient is ineligible or refuses to participate, the reason will be recorded in the log, if they so choose to provide us with reasons for the same.

In some cases, patients who have been discharged from the stroke units to the community may be identified as appropriate for the study. In this case the relevant Trust PI will provide them with the PIS and access for clarification.

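### The active-patient KPI is a bare count with no denominator, and no primary outcome has a precision statement, so meeting the KPIs does not measure acceptance

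*Combined protocol and SAP*

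**What the plan says.** Under Data Management and Statistical Analysis, the plan states that "a statistical analysis on the primary outcomes will not be conducted", because these outcomes are meant to evaluate impact and acceptance. The primary outcome is instead "considered good if planned KPIs are met or exceeded". The same section plans p values at the 0.05 level for the secondary outcomes.

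Primary Outcome Measures lists the targets:

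- "Total number of patients enrolled -> KPI: minimum 50 patients enrolled".
- "Total number of active patients -> KPI: minimum 40 active patients".
- Mean active weeks: total active weeks divided by patients enrolled, with "KPI: 8 weeks (excluding drop off before 4 weeks".
- Activity participation: "measured in average minutes per day dedicated to exercises with WeReha", with a KPI of 45 minutes per week.
- The number of drop-offs, the Technology Acceptance Model (TAM) questionnaire and the six age-sex groups have no KPI.

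Study Design sets no fixed sample size. Investigators recruit as many eligible patients as they can, using 75 devices that may each be issued twice. On uptake, it says: "A screening log will be used to track the number of patients that are approached to participate". No section plans a confidence interval, a standard deviation or a precision target for any primary outcome.

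**The concern.** Acceptance is the study's stated goal. Under Anticipated Results, the findings are to show impact on a large scale, to be collated with the other MAGIC-PCP trials and eventually to be compared with existing studies. Those uses need a rate or a mean with its uncertainty. A count that was reached is not enough, particularly when trials may enrol different numbers.

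As written, the verdict on the active-patient KPI does not depend on how many patients had to be enrolled to obtain 40 active ones. The same favourable verdict could describe a device that most enrolled patients kept using or one that about a quarter did. The secondary outcomes get inferential statistics, while the main question gets neither a rate nor an interval.

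**Working it through.** **Inputs.** At least 50 enrolled and at least 40 active (Primary Outcome Measures). 75 devices, each usable twice (Study Design), so at most 75 × 2 = 150 patients. The plan states no power, sample size calculation or precision to reproduce. The only derivable figure is the ratio of the two minimums, 40/50 = 80%, and the plan does not itself state that ratio.

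**Step 1: what 40 active patients means as a share.** The exact (Clopper-Pearson) 95% limits for x of n are the 0.025 quantile of Beta(x, n − x + 1) and the 0.975 quantile of Beta(x + 1, n − x).

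| Enrolled | Active | Share | Exact 95% CI |
|---|---|---|---|
| 50 | 40 | 80.0% | 66.3% to 90.0% |
| 75 | 40 | 53.3% | 41.4% to 64.9% |
| 100 | 40 | 40.0% | 30.3% to 50.3% |
| 150 | 40 | 26.7% | 19.8% to 34.5% |

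All four rows meet both count KPIs.

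**Step 2: how often the count rule is met.** With true active share p, P(X ≥ 40) = Σ C(n,k) p^k (1 − p)^(n − k), summed over k from 40 to n.

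| Enrolled | True share: probability that at least 40 are active |
|---|---|
| 50 | 70%: 0.079; 75%: 0.262; 80%: 0.584; 85%: 0.880 |
| 75 | 50%: 0.322; 60%: 0.902 |
| 100 | 30%: 0.021; 40%: 0.538; 50%: 0.982 |
| 150 | 25%: 0.348; 30%: 0.836; 40%: 1.000 |

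The share needed to meet the KPI falls steeply as enrolment rises.

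**Step 3: mean active weeks.** The plan gives no SD, so precision can only be shown under assumption. With n = 40, the 95% half-width is t(0.975, 39) × SD/√40. SDs of 3, 4, 5 and 6 weeks give about 1.0, 1.3, 1.6 and 1.9 weeks around the KPI of 8.

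The denominator is also unsettled, because the text divides by all enrolled while the KPI leaves out drop-offs. Suppose 50 enrol and 40 active patients average exactly 8 weeks, a total of 40 × 8 = 320. The other 10 have 0 to 3 active weeks each, so they add 0 to 30. Excluding drop-offs, the mean is 8.0. Over all enrolled it is 320/50 = 6.4 to 350/50 = 7.0.

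**Step 4: minutes.** The measure is per day and the KPI is per week. It is taken in active weeks only, and an active week already requires three sessions of at least 15 minutes, so 3 × 15 = 45. Read per week, the KPI is met by definition. Only the estimate and its interval carry information.

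**Step 5: TAM.** Annex B has 22 items on a scale of 1 to 7 and no scoring rule. Items 14 and 17 are worded negatively, so an unreversed mean would mix directions.

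**Step 6: groups.** An even split over six groups gives 50/6 ≈ 8, 75/6 ≈ 12 or 150/6 = 25 patients per group. The plan says that the actual distribution cannot be foreseen.

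**The case against.** The strongest reply is that this is a single-arm pilot whose device numbers are fixed by the funding project, so having no hypothesis test is defensible and the plan explains why. That stands. The gap is the missing estimates and intervals, not a missing test.

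A second reply is that enrolled, active and drop-off numbers will all be reported, so any reader can work out the share and its interval. That is largely true for active/enrolled and limits the harm. It does not help with the means, whose SDs are not planned for reporting, and it leaves the plan's own verdict independent of the share.

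A reader might infer more: that sampling error is wide enough to overturn a favourable KPI verdict. The documents do not support this. The KPIs are counts and means that are observed to be met or not, and 80% is never set as a threshold. Uncertainty matters once the result is read as an acceptance rate, and then mostly near the minimum. By contrast, 46 of 50 active has a lower exact limit of 80.8%.

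Two further inferences need limits. Groups of about 8 arise only at minimum enrolment with an even split, and the plan treats the groups as exploratory. The screening log is described for stroke-unit admissions. Whether it also covers patients identified in the community or volunteers is not stated, so it cannot be assumed to give the full uptake denominator.

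**Conclusion.** The point holds as a defect in what the trial will be able to conclude. If the plan is followed, it yields no planned acceptance rate and no precision for any primary outcome. The main weakness is the missing denominator: meeting the count of 40 is compatible with an observed active share anywhere from 26.7% (150 enrolled) to 80% or more (50 enrolled). Imprecision at a given enrolment comes second: 40 of 50 has limits of 66.3% and 90.0%.

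These figures rest on three assumptions. The first is that enrolment lies between the KPI minimum of 50 and the device ceiling of 150, which is a capacity and not a forecast. The second is that patients are independent with a common active probability. The third is that 80% is only the ratio of the two minimums. The half-widths for active weeks depend on the assumed SDs.

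**What to change.** Replace the sentence that excludes analysis with: *No hypothesis test is planned; primary outcomes are reported as estimates with 95% confidence intervals.* Then specify:

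- Active/enrolled with an exact CI, shown next to the KPI count.
- Enrolled/approached with an exact CI for recruits covered by the screening log. Either extend the log to community and volunteer recruits or state that they are excluded from this ratio.
- Mean active weeks with a CI, after choosing one denominator (all enrolled, or excluding drop-offs).
- Mean minutes with a CI, after choosing one time unit.
- TAM mean with a CI, after reverse-scoring items 14 and 17 (8 minus the response).
- Age-sex groups described with intervals.

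The KPIs can remain as project targets, but acceptance should be concluded from the active share and its interval.

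The cost is a little more analysis and a less favourable-looking statement if the result falls near the KPI minimum. The usage and questionnaire data are already collected. Only the optional extension of the log adds any recording.
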